10.2 Risk of BPD

The preliminary effectiveness analysis will be on the risk of BPD which is provided by BPD estimator. The risk of BPD is presented as a % and the dichotomized the outcome will be used in the analysis (none-mild vs. moderate-severe-death). The BPD outcome estimator uses the following information to provide individual risk of BPD:

1. Gestational age (weeks)
2. Birth weight (g)
3. Sex
4. Maternal Race/Ethnicity
5. Postnatal day
6. Ventilation type (on the postnatal day of interest)
7. F_iO_2 (%) (on the postnatal day of interest)

For example, a 25 week Hispanic female with birth weight of 689 g on postnatal day 14 on mechanical ventilation with a FiO_2 of 0.45 has risk of no BPD of 1.6%, mild 27.9%, moderate 28.9%, severe 30.5%, and death 11%. Thus, none-mild risk is 29.5% and moderate-severe-death risk is 70.5%.

The risk of BPD or death as defined by the NICHD Neonatal Research Network (NRN) BPD estimator will be evaluated at baseline, on days 7, 14, 21 and 28 of study drug, the postnatal days closest to these days will be used in the BPD estimator. The postnatal day will be re-grouped to fit the BPD estimator: day 0 and day 1 will be re-grouped as day 1, day 2 and day 3 as day 3, 4-7 days as day 7, 8-14 as day 14 and 15-21 as day 21. The BPD estimator includes infants up to 28 postnatal days; for infants older than that, the 28 day estimates will be used. The birth weight used in the BPD estimator is up to 1250g, for infants with birth weight greater than 1250g, 1250g will be used. The BPD estimator includes white, black, or Hispanic infants; infants with other race/ethnicity will be excluded from the estimation. Sensitivity analyses may be done by removing infants with birth weight greater than 1250g.

The change of risk of BPD (as a percentage) from baseline to the end of study (day 28 or LOCF) will be assessed using an analysis of covariance (ANCOVA) model, with percentage change from baseline as the dependent variable. Independent factors include baseline risk percentage and dose groups.

As an exploratory analysis, a longitudinal mixed effect model may be used to test the risk of BPD at baseline and days 7, 14, 21 and 28 (with no LOCF). This longitudinal analysis will use all available risk of BPD percentages at each time point. Fixed effects will include treatment groups, dose level and dosing days; random effects will include participant. Linear and nonlinear

trends of the drug effect for both overall and individual level data will be evaluated. An unstructured covariance matrix will be used initially to model the co-variance of repeated measures within participants, but other co-variance structures will be explored and the best structure will be chosen based on Akaike's Information Criteria.

Potential biomarkers (i.e. IL-1, IL-6, IL-8, TNF- α , and RANTES) may be included in the models mentioned above.

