1.1 Study Synopsis

Protocol Title	Safety of Furosemide in Premature Infants at Risk of Bronchopulmonary Dysplasia (BPD)
Phase:	II
Protocol Version	Version 5.0, 7 April 2015
Product	Furosemide
Objective	Primary: Describe the safety of furosemide in premature infants at risk of BPD Secondary: Preliminary effectiveness and pharmacokinetics (PK) of furosemide
Study Design	Multi-center, randomized, placebo-controlled, dose escalating, double masked, safety study

Study Population	
Inclusion Criteria
 
 1. Documented informed consent from legal guardian, prior to study procedures 2. Receiving positive airway pressure (nasal continuous airway pressure, nasal intermittent positive pressure ventilation, or nasal cannula flow > 1LPM) or mechanical ventilation (high frequency or conventional) 3. < 29 weeks gestational age at birth 4. 7-28 days postnatal age at time of first study dose 
Exclusion Criteria
 
 1. Exposure to any diuretic ≤ 72 hours prior to first study dose 2. Previous enrollment and dosing in current study, “Safety of Furosemide in Premature Infants at Risk of Bronchopulmonary Dysplasia” 3. Hemodynamically significant patent ductus arteriosus, as determined by the investigator 4. Major congenital anomaly (e.g. congenital diaphragmatic hernia, congenital pulmonary adenomatoid malformation) 5. Meconium aspiration syndrome 6. Known allergy to any diuretic 7. Serum creatinine >1.7 mg/dl < 24 hours prior to randomization 8. BUN >50 mg/dl < 24 hours prior to randomization 9. Na <125 mmol/L < 24 hours prior to randomization 10. K ≤2.5 mmol/L < 24 hours prior to randomization 11. Ca ≤ 6 mg/dL < 24 hours prior to randomization 12. Indirect bilirubin >10 mg/dl < 24 hours prior to randomization 13. Any condition which would make the participant, in the opinion of the investigator, unsuitable for the study 																												
Number of Participants	120																												
Number of Sites	Approximately 30 sites																												
Duration of Participation:	Up to 35 days (28 days of study drug plus 7 days of safety monitoring). Information about hospitalization will be collected at 36 weeks post menstrual age and/or at discharge.																												

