3.2 Selection of Study Population

Premature infants (inpatient in neonatal intensive care units) will be randomized 3:1 to furosemide: placebo with increasing target doses of furosemide for each Cohort. There will be 40 randomized and dosed participants in each Cohort for a total of up to 120 participants.

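### Section 10.2 rounds postnatal day up to the next estimator day and states no estimator day for days 22-27, although baseline can fall on any day from 7 to 28

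*SAP*

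**What the plan says.** Section 2.2.2.1 makes the change from baseline in the estimated risk of moderate-severe BPD or death the preliminary effectiveness outcome. Section 10.2 of the SAP says how that risk is obtained:

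- Timing: risk "will be evaluated at baseline, on days 7, 14, 21 and 28 of study drug", and "the postnatal days closest to these days will be used in the BPD estimator".
- Early bands: "day 0 and day 1 will be re-grouped as day 1, day 2 and day 3 as day 3".
- Later bands: "4-7 days as day 7, 8-14 as day 14 and 15-21 as day 21".
- Upper end: "The BPD estimator includes infants up to 28 postnatal days; for infants older than that, the 28 day estimates will be used".

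The Study Synopsis (section 1.1) admits infants at "7-28 days postnatal age at time of first study dose". The ANCOVA in section 10.2 takes the change from baseline to day 28 (or the last observation carried forward) as its outcome, with baseline risk and dose group as the independent factors. Postnatal age is not a factor.

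**The concern.** The list of bands stops at day 21 and the next rule starts after day 28. Days 22-27 lie inside the permitted entry range but have no stated estimator day. A programmer could use day 28 (continuing the pattern), day 21 (the last band named) or the nearer of the two, or could leave the value missing. Section 7 says that missing data will not be imputed in the non-PK analysis. A derivation rule should settle this before treatment is known.

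Where a band is stated, it always moves age upward. An infant assessed on postnatal day 8 is scored as if the same ventilation type and FiO2 had been observed on day 14, although day 7 is one day away. The shift depends on entry age, always runs in one direction, and enters the baseline value on which the change score and its covariate rest.

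**Working it through.** The SAP states no figure for this rule, so there is none to reproduce. The check lists the mapping over every permitted baseline day.

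**Inputs.**
- Baseline days 7 to 28, that is 28 − 7 + 1 = 22 days (section 1.1).
- Bands and upper-end rule as quoted from section 10.2.
- Estimator days in this range: 7, 14, 21, 28.
- N up to 120 (section 3.2).
- Assumption: the baseline assessment is on the day of first dose.

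**Mapping as written, beside the nearest estimator day.**

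| Baseline day | Day used as written | Nearest estimator day | Shift as written (days) | Distance to nearest (days) |
|---|---|---|---|---|
| 7 | 7 | 7 | 0 | 0 |
| 8, 9, 10 | 14 | 7 | +6, +5, +4 | 1, 2, 3 |
| 11, 12, 13, 14 | 14 | 14 | +3, +2, +1, 0 | 3, 2, 1, 0 |
| 15, 16, 17 | 21 | 14 | +6, +5, +4 | 1, 2, 3 |
| 18, 19, 20, 21 | 21 | 21 | +3, +2, +1, 0 | 3, 2, 1, 0 |
| 22, 23, 24 | none stated | 21 | – | 1, 2, 3 |
| 25, 26, 27 | none stated | 28 | – | 3, 2, 1 |
| 28 | 28 (implied) | 28 | 0 | 0 |

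- No stated day: 6 of 22 days.
- Stated day that is not the nearest: 6 of 22 days.
- Stated day equal to the nearest: 22 − 6 − 6 = 10 of 22 days.

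**Share of infants.** This needs an entry-age distribution, which the SAP does not give. Three assumed ones show the range. The early weights are 29 − d and the late weights d − 6 for day d; each set sums to 253.

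| Assumed entry age | Days 22-27 | Days 8-10 and 15-17 |
|---|---|---|
| Uniform | 6/22 = 27% (120 × 6/22 ≈ 33) | 6/22 = 27% (≈ 33) |
| Early-weighted | 27/253 = 11% | 99/253 = 39% |
| Late-weighted | 111/253 = 44% | 39/253 = 15% |

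**Where the grouping acts.** The youngest entrant is 7 days old. With first dose as study day 1, study day 28 falls on postnatal day 7 + 27 = 34 or later, so a completed day-28 endpoint always takes the 28-day estimate. The grouping choice then affects baseline only and cannot cancel in the change score.

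On-treatment visits also meet the gap. With first dose as study day 1, a day-7, 14 or 21 visit falls on postnatal days 22-27 for entry days 7, 9-14 and 16-21, which is 13 of 22. With first dose as day 0 it does so for entry days 8-13 and 15-20, which is 12 of 22. These visits feed the longitudinal model and any carried-forward endpoint.

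**Upward against nearest-day mapping, if the bands are completed with 22-28 as day 28.**
- Upward: each of the three seven-day bands contributes 6+5+4+3+2+1+0 = 21. The mean shift is 3 × 21/22 = 63/22 ≈ 2.9 days, all upward.
- Nearest: each seven-day block contributes absolute shifts of 1+2+3+3+2+1+0 = 12. The mean is 3 × 12/22 = 36/22 ≈ 1.6 days, with a net shift of zero.
- The two mappings differ on days 8-10, 15-17 and 22-24, which is 9 of 22 days (41%, about 49 of 120 if uniform).

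The 41% supposes that the bands are completed; the 27% for days 22-27 takes the text as it stands. They belong to different readings and must not be added.

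**The case against.** **The two sentences need not conflict.** A reader might infer that the closest-day sentence contradicts the bands. Up to that point section 10.2 has named only baseline and study-drug days, so these are the most natural reference. The sentence then chooses which postnatal day stands for each visit, which fits the one-day visit window in section 9.5, and the bands are a second step. This stands: the wording is ambiguous, not a proven contradiction.

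**Rounding up is not shown to be wrong.** A reader might infer that infants are scored on the wrong day. For days 0-21 the rule is explicit and reproducible, and nothing in the SAP says that nearest-day is the estimator's proper use. The bands may follow the estimator's own convention. This stands too. What can be said is that the day used is often not the nearest and always errs upward.

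**Days 22-27 need not go unscored.** Every listed band takes its upper bound and the estimator runs to day 28, so 22-28 as day 28 is the likely intent. Where section 10.2 excludes infants (other race or ethnicity), it says so. This stands: the defect is a missing rule, not a demonstrated loss of data.

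**The stakes are limited.** The mapping is the same in every arm, the primary outcome is safety, section 7 calls the analyses exploratory or descriptive, and section 10.1 also models BPD itself at 36 weeks. All true; no bias between arms is shown. However, cohorts enrol in sequence by dose (section 4.1) and the placebo infants are presented as one group (section 7). Randomization within a cohort therefore does not guarantee similar entry ages across dose levels, and the ANCOVA does not adjust for age.

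**Conclusion.** The point holds as an incomplete and one-sided derivation rule. Of the 22 permitted baseline days, 6 have no stated estimator day, and another 6 go to one that is 4-6 days later than true age when one lies 1-3 days away. These day counts follow from the text, given that baseline is the day of first dose. The shares of infants (11% to 44% for the gap, 15% to 39% for the non-nearest days) rest on assumed entry-age distributions.

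The consequence is avoidable age-dependent error in baseline risk, which serves as reference and covariate for the secondary effectiveness outcome. Its size in risk points is unknown, because the estimator's equations are not in the SAP. The documents do not support a claim that the effectiveness comparison is biased. The point is worth correcting because the correction is nearly free.

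**What to change.** Before unmasking, put one complete mapping in section 10.2. The preferred version is the nearest estimator day: postnatal days 7-10 as day 7, 11-17 as day 14, 18-24 as day 21, and 25 or later as day 28. State that the closest-day sentence concerns which postnatal day represents each study visit, and that the mapping to an estimator day is a separate step.

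If the upward bands are kept to match the estimator's own convention, say so, add 22-28 as day 28, and run the nearest-day mapping as a sensitivity analysis of the ANCOVA.

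Either version closes the gap at baseline, at on-treatment visits and for carried-forward values. The cost is a few lines of SAP text and one recoded derivation, with no new data.

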9.5 Special Safety Events of Interest

Hearing Loss

Hearing loss will be identified by hearing test (e.g. BAER) prior to discharge. Any failure of the hearing test (unilateral or bilateral) will be considered as hearing loss. If multiple tests are done, the last test post last study dose will be considered as the final result and any positive result during the study period will be reported. If only one hearing test is obtained, it can be considered as a final result if it was performed after the last study dose.

Nephrocalcinosis/nephrolithiasis

Nephrocalcinosis/nephrolithiasis will be determined by renal ultrasound. The summary will include nephrocalcinosis, nephrolithiasis and any of nephrocalcinosis or nephrolithiasis. A renal ultrasound is required per protocol at final study assessment. Results of standard of care renal ultrasounds will also be collected during the treatment period, follow-up period, 36-week PMA assessment. The study central radiologist (CR) will review any positive findings for nephrocalcinosis / nephrolithiasis reported by the site. If the primary study CR CONCURS with the site radiologist's findings, study image results will be documented and no further action will be taken; otherwise, a secondary study CR will review the images for final determination of results. Majority rules from up to 3 reviewers will be applied for the final renal ultrasound results. If multiple ultrasounds are received, the last ultrasound that is available post last study dose will be considered as the final result. If only one ultrasound is obtained, it can be considered as a final result if it was performed after the last study dose. In addition, any positive findings during the study period will be summarized as a separate endpoint.

Hearing loss, nephrocalcinosis and nephrolithiasis event rates will be summarized by dose groups and the percentage of participants with these events may be compared using a Fisher's exact test.

Respiratory assessment

The following information will be collected at baseline, on day 7, 14, 21, and 28 (+/- 1 day) of study drug administration, once during the follow-up period, once at 36 weeks PMA, and once at discharge:

1. Maximum F_iO_2 (sustained for > 30 minutes to account for suctioning, unless it is known to be a temporary (<2 hour) increase in F_iO_2)
2. Ventilation type:
 - a. High frequency ventilator
 - b. Conventional mechanical ventilator

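### Every observed day-28 BPD risk value lies beyond the estimator's 28-day age limit, and neither model in SAP 10.2 includes age at entry

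*SAP*

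**What the plan says.** The synopsis (SAP 1.1) sets eligibility at "7-28 days postnatal age at time of first study dose". Under SAP 10.2 the estimated risk "will be evaluated at baseline, on days 7, 14, 21 and 28 of study drug". SAP 9.5 collects the respiratory inputs "on day 7, 14, 21, and 28 (+/- 1 day) of study drug administration".

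The estimator takes postnatal day as one of its seven inputs. SAP 10.2 bands that input: 4 to 7 days count as day 7, 8 to 14 as day 14, and 15 to 21 as day 21. Beyond the upper limit the rule is: "The BPD estimator includes infants up to 28 postnatal days; for infants older than that, the 28 day estimates will be used".

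The main analysis of this endpoint is the change in risk "from baseline to the end of study (day 28 or LOCF) will be assessed using an analysis of covariance (ANCOVA) model". Its terms are stated briefly: "Independent factors include baseline risk percentage and dose groups". For the optional longitudinal model, "Fixed effects will include treatment groups, dose level and dosing days; random effects will include participant".

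One sensitivity analysis is named for an input beyond the estimator's limits, and it concerns weight: "Sensitivity analyses may be done by removing infants with birth weight greater than 1250g". No counterpart is named for age.

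**The concern.** The substitution rule reads like a provision for a few older infants. Set beside the entry window, it covers every infant assessed at study day 28. The endpoint value is then a prediction made with a day-28 equation from the support an infant needs at about five to eight weeks of age.

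The baseline value, in contrast, uses an equation that depends on how old the infant was at entry. Take two infants whose ventilation type and FiO2 stay constant. If one enters at day 25 and is scored with the day-28 equation both times, all seven inputs are the same and the change is zero. If the other enters at day 7, the equation differs between baseline and day 28, and the change need not be zero. Part of the change score therefore reflects entry age and not respiratory course.

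Two things are at stake. One is the meaning of the absolute change within a group. The other is the cleanness of the dose comparisons, because entry age adds variation to the outcome and could differ between cohorts enrolled at different times.

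**Working it through.** The SAP gives no age range for the day-28 values, so there is no stated figure to reproduce.

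**Inputs**
- Entry age: 7 to 28 days, which is 22 whole-day values (SAP 1.1).
- Assessments: study days 7, 14, 21 and 28 (SAP 10.2), within one day either side (SAP 9.5).
- Estimator limit: 28 postnatal days (SAP 10.2).
- Day counting: not stated in the SAP, so both conventions are shown.

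**Step 1. Age at assessment**

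If the first dose is day 1, age = entry + study day − 1. If it is day 0, age = entry + study day.

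At study day 28:
- day-1 counting: 7 + 27 = 34 up to 28 + 27 = 55;
- day-0 counting: 7 + 28 = 35 up to 28 + 28 = 56;
- extremes with the visit window: 34 − 1 = 33 and 56 + 1 = 57.

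Even the youngest case, 33 days, is 5 days past the limit.

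**Step 2. Entry ages still in range (age ≤ 28, nominal day)**

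| Study day | First dose = day 1 | First dose = day 0 |
|---|---|---|
| 7 | 16 of 22 | 15 of 22 |
| 14 | 9 of 22 | 8 of 22 |
| 21 | 2 of 22 | 1 of 22 |
| 28 | 0 of 22 | 0 of 22 |

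These are counts of possible entry ages, not of infants, because the SAP gives no distribution of entry age. The day-28 row needs no distribution. The earlier rows show that a value carried forward from days 7 to 21 can be in range.

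**Step 3. Change of equation between baseline and day 28**

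Baseline is taken as the day of first dose.
- Entry at 7: day-7 equation (1 entry age).
- Entry at 8 to 14: day-14 equation (7).
- Entry at 15 to 21: day-21 equation (7).
- Entry at 22 to 28: day-28 equation (7). This is an assumption, since the banding does not assign ages 22 to 27.

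The endpoint at study day 28 always uses the day-28 equation. So 1 + 7 + 7 = 15 of 22 entry ages change equation and 7 of 22 do not. If ages 22 to 24 went instead to the nearer of days 21 and 28, which is day 21, the count would be 15 + 3 = 18 of 22. Either way, some infants change equation and some do not, and entry age decides which.

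**Step 4. Model terms**

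The ANCOVA has baseline risk and dose group. The mixed model has treatment group, dose level, dosing day and participant. Neither has entry age or postnatal age. Baseline risk contains postnatal day, but only after banding and combined with gestational age, birth weight, sex, race/ethnicity, ventilation type and FiO2. Infants of different entry ages can therefore share the same baseline risk.

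**Step 5. Protection from randomisation**

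Allocation is 3:1 within each cohort of 40 (SAP 3.2), and cohorts enrol one after another (SAP 4.1). Each cohort has 10 placebo infants (SAP 1.1), and SAP 7 reports a single placebo group. A contrast between dose levels, or between one dose level and pooled placebo, therefore crosses enrolment periods and is not fully randomised. The ANCOVA as listed has no cohort term.

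**The case against.** The strongest reply is that the SAP states the limit openly and fixes a rule that is the same in all arms. At study day 28 every infant is scored with one equation, so differences there come from support and birth factors. Entry age already enters through baseline risk. The outcome is secondary and preliminary, and SAP 7 calls the analyses exploratory or descriptive. Most of this stands. It shows that this is a weakly fixed endpoint and not an error, and that no confirmatory claim depends on it. It does not remove the dependence of the change score on entry age.

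A reader might go further than the document allows in four ways.

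- **That no planned analysis avoids the extrapolation.** This is true only of the estimator analyses in 10.2. SAP 10.1 analyses observed BPD at 36 weeks PMA without the estimator, and SAP 9.5 summarises the respiratory assessments directly. SAP 10.1 is, however, a separate endpoint that classifies BPD among survivors, and not a sensitivity analysis of this one.
- **That every endpoint value is out of range.** Step 2 shows that carried-forward values may not be. The ANCOVA can therefore mix in-range and substituted values.
- **That age is a worse extrapolation than birth weight.** The SAP gives neither the share of infants above 1250 g nor the estimator's sensitivity to either input, so the two cannot be ranked.
- **That an in-range-only ANCOVA should be required.** Using the last assessment at or before postnatal day 28 would omit 6 or 7 of the 22 entry ages. Of those kept, 14 of 16 (day-1 counting) or 14 of 15 (day-0 counting) would be measured at study day 7 or 14. That is mostly a one- to two-week contrast in early entrants, and does not check the 28-day contrast.

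**Conclusion.** The point holds in a limited form. That all observed day-28 values are substituted follows from the SAP's own figures under either day count and anywhere in the visit window. That 15 of 22 entry ages change equation rests on giving ages 22 to 28 the day-28 equation, and on baseline falling on the day of first dose. The dependence of the change score on entry age follows from both facts, and baseline risk adjusts for it only indirectly.

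The consequence is harder interpretation of each group's absolute change and some added variation in the contrasts. The SAP supports no figure for the size of that variation, because it gives neither the estimator's equations nor the distribution of entry age. Bias in the dose contrasts is a possibility only, and would need entry age to drift across cohorts. The document does not show that it does. The change is worth making because it is nearly free, not because the planned analysis is invalid.

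**What to change.** Keep the planned endpoint and amend SAP 10.2 as follows.

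1. Add baseline postnatal age as a covariate to the ANCOVA, beside baseline risk and dose group, and to the mixed model if it is used. SAP 8.2 already lists postnatal age among the baseline variables. A linear term costs one degree of freedom.
2. Report by dose group the number and share of endpoint values that used the substituted 28-day estimate. Carried-forward in-range values will then be visible.
3. State that the estimator result will be interpreted beside observed moderate-severe BPD or death at 36 weeks PMA. BPD (SAP 10.1) and death (SAP 2.2.3) are both already assessed, so this needs one combined tabulation and no new data.

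The limits are modest but should be understood. A linear age term only approximates a stepwise change of equation. It guards against drift in entry age but not against other differences between cohorts, and it does not make the day-28 values in range. Items 2 and 3 are there for that reason. The cost is a few lines of SAP text and minor programming.

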2.2.2 Secondary Outcome Measures

2.2.2.1 Preliminary effectiveness: Risk of BPD

The outcome measure is change in moderate-severe BPD or death risk from baseline. Moderate-severe BPD or death risk will be defined by the NICHD Neonatal Research Network BPD outcome estimator⁴. (<https://neonatal.rti.org/index.cfm?fuseaction=BPDCalculator.start>).

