7 GENERAL ISSUES FOR STATISTICAL ANALYSIS

Descriptive statistics such as number of observations, mean, median, standard deviation, standard error, minimum and maximum will be presented by dose groups for continuous variables (such as age, weight, etc.). The dose groups will include furosemide groups (by dose level and across all dose levels), placebo group and overall. Other descriptive statistics such as counts, proportions, and/or percentages will be presented by dose groups to summarize discrete variables (such as race, sex, etc.).

Missing data will not be imputed in the non-PK analysis of this study.

Patient profile graphs showing chronologically the dosing, PK sampling, laboratory results of interest, risk of BPD, and adverse events for each participant will be developed.

All confidence intervals and tests will use $\alpha=0.05$. Analyses in this study are exploratory or descriptive in nature. No adjustments for multiplicity between endpoints are planned. Analyses will be performed using SAS Software version 9.2 or later.

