8 STUDY PARTICIPANTS AND DEMOGRAPHICS

8.1 Disposition of Participants and Withdrawals

All safety participants will be accounted for in this study. Number and percentage by Cohorts and dose groups for the safety population and PK population will also be presented. Also, summaries will include the number and percentage of participants who completed or early terminated the study, classified by reasons for early termination; the number of participants from each study site; and the number and percentage of participants who completed or early terminated the study at each study site. Early termination is defined as:

1. Participant is randomized but does not receive at least 7 days of study product.

2. Participant receives 7-28 days of study product, but does not complete required follow up assessments.

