10 EFFICACY ANALYSES

10.1 Incidence of BPD

BPD will be defined by the NICHD BPD estimator as a dichotomous (none-mild vs. moderate-severe) variable and as a categorical variable (none, mild, moderate, or severe) among survivors by modifying the NIH consensus definition of BPD to include infants transferred prior to 36 weeks and the need for oxygen at 36 weeks PMA (or discharge, if sooner than 36 weeks PMA). The severity of BPD is defined as follows:

1. **No BPD:** receiving > 21% supplemental oxygen (O_2) for ≤ 28 days and not at 36 weeks PMA
2. **Mild BPD:** receiving > 21% O_2 for ≥ 28 days but not at 36 weeks PMA
3. **Moderate BPD:** receiving > 21% O_2 for ≥ 28 days plus treatment with <30% O_2 at 36 weeks PMA

4. **Severe BPD:** receiving $> 21\% \text{ O}_2$ for ≥ 28 days plus $\geq 30\% \text{ O}_2$ and/or positive pressure at 36 weeks PMA

Note that the day in the definition above is postnatal day but not treatment day. Final assessment of BPD at 36 weeks PMA will be summarized by dose groups.

BPD will be evaluated through logistic regression models by whether the event occurred or did not occur at 36 weeks PMA assessment. Independent factors in the model will include gestational age, birth weight, dose groups. Confidence intervals will be calculated using the profile-likelihood.

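### Section 7 bars imputation although the 10.2 ANCOVA uses LOCF, and LOCF leaves an infant who dies before day 28 at the last predicted risk

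*SAP*

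**What the plan says.** - **Section 7 (general issues):** "Missing data will not be imputed in the non-PK analysis of this study". No exception is given.
- **Section 10.2, ANCOVA:** "The change of risk of BPD (as a percentage) from baseline to the end of study (day 28 or LOCF) will be assessed". The abbreviation list expands LOCF as last observation carried forward. The model adjusts for baseline risk and dose group. Table 14.2.2 places it in the safety population, that is, every infant randomized and dosed.
- **Section 10.2, mixed model:** an optional exploratory analysis may "test the risk of BPD at baseline and days 7, 14, 21 and 28 (with no LOCF"). It uses only the values available at each time point.
- **Outcome:** Section 2.2.2.1 says "The outcome measure is change in moderate-severe BPD or death risk from baseline". Section 10.2 says that the dichotomized outcome "will be used in the analysis (none-mild vs. moderate-severe-death").
- **Section 10.1:** observed BPD is graded "as a categorical variable (none, mild, moderate, or severe) among survivors".
- **Assessment times (Section 9.5):** respiratory data are taken at baseline and "on day 7, 14, 21, and 28 (+/- 1 day) of study drug administration, once during the follow-up period".

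No section says what value an infant who dies before day 28 receives in the ANCOVA.

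**The concern.** There are two problems.

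First, carrying a value forward is imputation, and the ANCOVA is not a PK analysis. A programmer who follows Section 7 drops infants whom 10.2 keeps.

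Second, death belongs to the outcome whose risk is analysed, yet a death is handled like any other missing value. An infant whose predicted risk fell before death counts as improved. An infant who dies before the day-7 assessment has only a baseline value, so the change is 0 or the infant is left out; 10.2 does not say which. Following Section 7 instead leaves the death out altogether.

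The other efficacy analyses do not make up for this. Section 10.1 has no death category, and the mixed model is optional and uses available values only. The ANCOVA is the only non-optional analysis of the preliminary effectiveness outcome. In a dose-escalation trial, a dose group with more early deaths would look better there than if death counted as the event.

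**Working it through.** **Which rule is meant.** Section 10.2 uses LOCF for the ANCOVA and explicitly switches it off for the mixed model. LOCF is therefore deliberate, and Section 7 is the text to correct.

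**The SAP's example infant.** None-mild risk is 1.6 + 27.9 = 29.5%, so moderate-severe-death risk is 100 - 29.5 = 70.5%, as stated. The listed parts add to 28.9 + 30.5 + 11 = 70.4%, which is rounding.

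**One infant.** Take a baseline of 70.5%, a last value of 50% (assumed), then death.
- LOCF: 50 - 70.5 = -20.5 points, an improvement.
- Death scored as 100%: 100 - 70.5 = +29.5 points.
- Difference: 50 points, which is 100 minus the last risk.

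**Group mean.** For a group of n infants with d deaths, LOCF lowers the mean change, relative to the 100% score, by d x (100 - last risk)/n. Dose groups have n = 30; placebo is 3 x 10 = 30.

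| Last risk | 1 death | 2 deaths | 3 deaths |
|---|---|---|---|
| 80% | 0.67 | 1.33 | 2.00 |
| 70.5% | 0.98 | 1.97 | 2.95 |
| 50% | 1.67 | 3.33 | 5.00 |

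Read as excess deaths over placebo at equal last risks, the table gives the shift in the raw contrast. The shift is 0 if deaths and last risks are equal. Section 10.2 excludes some infants by race/ethnicity; if that left 25 in a group (assumption), one death would count 0.80, 1.18 or 2.00 points.

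**Number of deaths.** The SAP gives no death rate. Its only figure is the 11% death component for one ventilated example infant. Applied to a whole group this is 0.11 x 30 = 3.3 deaths, but it is one infant's prediction and is not stated to be a 28-day risk.

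**Does baseline adjustment remove the shift?** This was simulated with assumed inputs: four groups of 30; baseline risk with mean 60 and SD 15, limited to 10-95; change with mean -5 and SD 15; deaths drawn with probability proportional to baseline cubed; ANCOVA on baseline and group; 1,500 runs per setting.
- With 2, 3 or 4 deaths against 1, the adjusted contrast shifts by about 1.2, 2.5 and 3.6 points. The raw formula gives 1.2, 2.4 and 3.6.
- With 2 against 2, the shift is 0.0.
- The 95% half-width is about 7.5 points under LOCF and 8.3 to 8.6 with deaths at 100%. With SD 20 it is about 9.7 and 10.3 to 10.5.
- Dropping the deaths gives contrasts within 0.1 point of LOCF, because pre-death changes were assumed to resemble those of survivors.

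Adjustment does not remove the shift. It stays below the half-width in these settings.

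**Wording of the dependent variable.** Section 10.2 calls it percentage change; Section 2.2.2.1 and the title of Table 14.2.2 say change. A move from 70.5% to 50% is -20.5 points, or (50 - 70.5)/70.5 = -29.1% as relative change.

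**The case against.** The outcome is a predicted risk, not an observed event. The moderate-severe-death label says which predicted probabilities are summed, and the carried value already includes a death component. A survivor who later develops severe BPD also keeps the predicted value, so LOCF treats observed death and observed BPD alike. Scoring death as 100% mixes observed deaths with predictions. **This stands.** It means that the SAP does not compel the 100% score as the main analysis.

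The size also depends on the last risk. The simulation implies a mean last risk near 64% in infants who die (100 - 1.2 x 30). If risk rises before death, LOCF captures part of that: at 90% the shift is 10/30 = 0.33 points per death. **This stands too**, and it is why a range is given.

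Deaths are not lost from the report. Section 2.2.3 lists death as an outcome, and Section 9.1 makes death at or before 36 weeks PMA a serious event, tabulated by dose group. **This stands** and limits the consequence.

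The conflict with Section 7 can be called a drafting slip, since a specific rule overrides a general one. That settles which rule was meant, but Section 7 is still wrong as written. It also does not answer the second problem, because the specific rule is the one that can record a death as an improvement.

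**Conclusion.** The point holds in a limited form. Sections 7 and 10.2 contradict each other. LOCF, as the only stated rule, lets a death before day 28 count as no change or as an improvement. Against a score of 100%, each death lowers a 30-infant group's mean change by about 0.7 to 1.7 points for last risks of 80% to 50%, and by 0.98 at 70.5%. The last risks are assumptions apart from the SAP's example, and the number of deaths is unknown.

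A reader might infer more, in two ways that the document does not support:
- **That LOCF is simply wrong and 100% must replace it.** The endpoint is a predicted risk, so this is a choice of estimand.
- **That the effectiveness comparison is invalid or that deaths are concealed.** A contrast moves only with an imbalance in deaths or last risks. The simulated shift is below the half-width, Section 7 calls the analyses exploratory or descriptive, and deaths are reported elsewhere.

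It should still be fixed: when deaths are imbalanced, a group with more deaths looks better, and the remedy is cheap. The percentage-change wording is a clarification only.

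**What to change.** 1. **Section 7:** add an exception to the no-imputation sentence for LOCF as stated in 10.2.
2. **Section 10.2:** separate death from other missing day-28 values. Pre-specify a required ANCOVA in which an infant with a baseline estimator value who dies before the day-28 assessment is scored as 100% risk. An infant already assessed at day 28 keeps the observed value, which matters because of the one-day window in 9.5. Say how day 28 is counted for an infant who has stopped study drug.
3. **Reporting:** show this analysis beside the LOCF ANCOVA, with the number of deaths by dose group. Which of the two is the main analysis is the sponsor's choice, to be fixed before unmasking. LOCF can stay for day-28 values missing for other reasons.
4. **Clarification:** state that the dependent variable is change in percentage points.

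**Cost:** a few sentences of SAP text and a few lines of code. Deaths can be identified from the serious-event data under 9.1. The downside is that the 100% analysis mixes observed deaths with predicted risks and has a somewhat wider interval. Reporting both analyses shows how far the result depends on the choice.
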